- 4) *Psychological distress or retribution*: Thus are concerns including risk of retribution against perpetrators disclosing in these studies. The risk of retribution against boys disclosing perpetration is guarded against by using self-completion for disclosure of acts that are socially stigmatizing or involve violence. The other concern is psychological distress; those who have raped or perpetration sexual assault can find discussing it makes them realize that it was wrong. The scientific team has extensive experience in interviewing participants, including adolescents around these topics and rarely have participants reacted to these types of questions with more than temporary embarrassment or mild discomfort in group discussion because they can decide what to discuss. For other data collection, we gather data using sensitive self-report methods including anonymized surveys and ACASI. The scientific team will train and supervise the RAs in these

procedures and techniques to gather data sensitively. If any such moments of sensitivity occur during the study, the M-PIs will be available for consultation. Further, if participants experience emotional discomfort, they will be given the option of taking a break or rescheduling the focus group discussion or other data collection for another date and time. Further, any distress will be minimized by assurances that participants can refuse to answer any particular question they do not feel comfortable addressing and withdraw from the study at any time without penalty. For consent and assent procedures for Aims 1, we will spend significant time discussing what topics will be covered, particularly highlighting what questions will explore including HIV-status, perpetration behaviors. We will emphasize that adolescents can halt participation at any time without consequence. We will also emphasize that although study staff will protect confidentiality of participants, this is not guaranteed in group settings. We also highlight the legal norms that would require break in confidentiality, and who information would be reported to as laid out by South African law. We balance these legal norms from South Africa on protecting the best interests of the child. For some data, we collect it anonymously (as in the school climate survey in Aim 2), participants will be guaranteed that the information will be kept confidential with no reporting given the anonymized data. In other cases of data for our other Aims, we follow the limits to confidentiality detailed above. Although our study protocol does not specifically probe for identifiable victims of perpetration, we recognize that there is the small chance adolescents will disclose this, unprompted by our team and requiring reporting. In anticipation of any possibility of serious adverse events, we will refer adolescents to appropriate HIV support, mental health, and social support services, and for various psychological issues to the specific DCAPs within catchment areas after gaining permission for research from the Department of Education. In our weekly team meetings, we explicitly probe for any unanticipated ethical situations which do not need immediate emergency attention. All ethical emergencies requiring urgent attention are reported to the PIs immediately. All procedures will be reviewed by institutional IRBs.

Planned Procedures for Protecting Against or Minimizing Potential Risks

Overview. For adolescents, during assent procedures, and for parents during consent procedures, we highlight the legal norms that would require break in confidentiality, and who information would be reported to. For both adolescents in focus groups, we will minimize loss of privacy by limiting access to individually identifiable information using unique RINs on all paper, electronic data, and analyses. Electronic data, including digital voice recordings and data collected via ACASI will have several protections. First, all data will be stored on password-protected computers including smartphones and files. Second, all files on project computers and android smartphones will be further protected by nCrypted Cloud software which offers two-way encryption with secure access controlled by PIs (who can turn on and off access to password protected files from a central location) and wipe all data from devices remotely in the case of theft. NCrypted Cloud also enables the PIs to control who has access, who can move files from the secured and encrypted cloud serve onto local hard drives (including computers, smartphones, and external harddrives), and whether and how files can be moved between providing absolute control over data management and monitoring. Third, all staff will be trained in procedures for maintaining confidentiality of participant information. We are also prepared to address any distress that may arise by referring to South African's mental health care within their free public health systems. All serious adverse events will be reported to IRB and NIH. Overall internal monitoring of the safety of human subjects will be conducted by the M-PIs. For non-emergency issues, a weekly meeting will be held to address study progress, recruitment and retention, data collection, and other factors related to human subjects and meetings will be held more often if necessary.

Unanticipated Problems or Adverse Events. If an Unanticipated Problems or a Serious Adverse Event occurs at the study site and is more likely than not related to the research activity, and places participants or others at a greater risk of harm than was previously known or recognized, the M-PIs will report the event in writing using the appropriate forms to IRB. The M-PIs will also report Serious Adverse Events in writing to the sponsor. The M-PIs will review the Adverse Event report with the entire study team and gather any information needed to investigate the event and to determine subsequent action. The M-PIs will document and report any subsequent action to IRBs. We will also generate a brief report of Adverse Events for the study record each year, and we will forward the report to Brown University IRB, SA MRC HREC, and NIH.

Potential Benefits of the Proposed Research to Human Subject and Others. There may be little or no direct benefit to participants from the study. Some possible benefits may include informing HIV and IPV prevention science. Adolescent participants will be given information on HIV, IPV, general health, and social services and referrals if necessary. The risks associated with this research are reasonable in relation to the anticipated benefits of advancing empirical knowledge adolescent prevention approaches for this high priority population and setting.

Importance of Knowledge to be Gained. To our knowledge, this will be the first intervention to prevent adolescent HIV risk and IPV perpetration in an integrated manner and in a high impact setting (South Africa).

Data and Safety Monitoring Plan

Data Protected by Unique Research ID Number (RIN). Every individual that expresses interest in our study and is deemed eligible will be assigned a RIN. All data they provide will be identifiable only by the RIN, which will not contain any personal identifiers. During this study, we will take precautions to separate any documents that identify participants by name from documents that contain participant data. Documents that identify participants by name will include the password-protected file containing participants' signed informed consent/assent forms and signed documentation that participants have received reimbursement. These documents will be kept entirely separate from any documents containing participant data. Paper documents that identify participants by name will be kept in locked cabinets in the offices of study personnel. Data will also be backed up on a weekly basis and transferred via two-way encryption via the nCrypted Cloud program for PIs and Co-I to oversee for quality control. Participants' names will never appear in any report resulting from the project.

Electronic data, including digital voice recordings and data collected via ACASI on android smartphones will have several protections. First, all data will be stored on password-protected computers and phones and files on these electronic devices will store data within electronic files that are further protected via nCrypted Cloud, approved by Brown's Computing, including their information security division. NCrypted Cloud software offers two-way encryption with secure access controlled by M-PIs (who can turn on and off access to password protected files from a central location) and wipe all data from devices. NCrypted Cloud also enables the M-PIs to control who has access, who can move files from the secured and encrypted cloud serve onto local hard drives (including computers, smartphones, and external hard drives), and whether and how files can be moved between providing absolute control over data management and monitoring. Third, all staff will be trained in procedures for maintaining confidentiality of participant information. Fourth, audiotapes will be transferred to a secure computer within 48 hours of recording. Encrypted data on the nCrypted Cloud server can be downloaded daily from any location in the world (via secure password) and if authorized by the PIs, saved to password protected hard-drives on computers dedicated solely to the project. Data analyses will only focus on data associated with RIN. All other identifiers will be expunged from transcripts. Any names or pseudonyms used during focus groups will be replaced with the RIN. To guard against accidental data loss, the project data will be backed up onto a secure server weekly.

Encouraging Focus Group Participants to Maintain Confidentiality. At the start of each focus group, we will emphasize the need for confidentiality and discuss the need for participants to refrain from sharing others' comments with any other person after the group ends. We cannot completely safeguard the confidentiality of participants' statements during focus group sessions, because these sessions involve multiple participants. We will state this fact explicitly when we obtain informed consent and assent from focus group participants. We will strongly encourage focus group participants to use aliases during the group discussion to protect their names.

Training in Confidentiality. The M-PIs will provide the study team with training in all ethical procedures including informed consent/assent, maintaining confidentiality, and protecting confidential data. This training includes for example, the importance of securing participants' privacy, the separation of data from identifiers, and protocols for using locked offices, filing cabinets, and password-protected files to avoid unauthorized use of participant data. The study team will meet regularly to discuss protocols for maintaining participants' privacy. The study team will also follow institutional policies at Brown University for requiring mandatory training in human subjects protection before conducting any study activities.

Protocols for Audio Files. Focus group discussions will be recorded on digital voice recorders. Given our precautions to maintain confidentiality, the risk of a confidentiality breach related to recorded data is minimal, and that it is reasonable in relation to the benefits to be gained by recording focus groups. This risk is also reasonable in relation to the importance of the knowledge to be gained from our study. After each day of recording, the group facilitator will transfer all new recordings to a project drive on a password-protected computer. He or she will label files with the number of each focus group and ensure that files are password-protected. To guard against accidental data loss, the project data will be backed up weekly. All original recordings will be removed from the digital voice recorders immediately after transferring the recording to a password protected and secure project drive and before starting a new focus group. Transcript files will also be stored securely in password-protected files, on password-protected computers. The transcript file has been "cleaned" after it has been reviewed by project staff who participated in the focus group for accuracy, and to expunge any identifying information other than a participant's RIN (e.g., name, address, name of school, etc.). After a transcript file has been "cleaned", this will be the primary document for analysis in NVIVO. RAs will receive ongoing supervision and training in regular meetings, which will also ensure continued compliance with data safety protocols. The M-PIs will be responsible for ensuring that study protocols for maintaining confidentiality are followed. Serious adverse events will be reported to and written reports will also be provided NIH.

Data and Safety Monitoring. Aim 1 is comprised of qualitative focus groups. Aim 2 is an open pilot of our intervention to assess acceptability. Aim 3 is a randomized controlled pilot trial of our intervention to assess feasibility. For both Aim 2 and Aim 3, this is a pilot of a prevention trial (thus not a treatment) and not requiring interim analysis for safety and monitoring. Thus our focus is on identifying Unanticipated Problem or a Serious Adverse Events that may occur at the study site and is more likely than not related to the research activity, and places participants or others at a greater risk of harm than was previously known or recognized.

M-PIs are responsible for monitoring the safety and efficacy of this trial and complying with the reporting requirements. The safety of participants will be monitored during each contact with study participants. There will also be regular team meetings monitoring of the safety of participants. If Serious Adverse Events, Unanticipated Problems occur, M-PIs will report the event in writing using the appropriate forms to IRB. For Serious Adverse Events that require clinical care, referral for appropriate care for subjects will be conducted for them to access care within South Africa's free at point of care public health care system.

The M-PIs will review the Adverse Event report with the entire study team and gather any information needed to investigate the event and to determine subsequent action. The M-PIs will document and report any subsequent action to IRBs. We will also generate a report of Adverse Events for the study record each year, and we will forward the report to Brown University IRB, SA MRC HREC and NIH.

G. MANAGEMENT DETAILS

Staff and Scientific Collaboration

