We also address peer-level factors in our prevention model. At the peer level we use bystander intervention techniques.⁸⁶⁻⁹⁰ Positive peer pressure – as exerted through prosocial bystander action – can prevent IPV in others. Importantly, bystander behaviors can also reinforce the bystanders own prevention behaviors. The bystander approach has promise in correcting misperceptions about IPV^{91,92} and decreasing personal engagement in IPV, interpersonal violence, and aggression.²³ This aspect of the violence prevention model is aligned with the “M-motivation” component of the HIV prevention theoretical model because bystander actions involve social learning where peer reinforcement results in self- and social-rewards for positive behaviors. We also build self-efficacy and behavioral skills, including for example, practice in assertive bystander communication (e.g., what to say, how to say it) and behavioral action (e.g., confronting and halting IPV behavior of peers, knowing who to contact for reporting and help in the case of suspected or actual IPV, linking peers and potential victims to appropriate services). This aspect of the violence prevention model is aligned with the “B-Behavior” component of the HIV prevention theoretical model.

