Design. This is a randomized controlled trial where participants are prospectively assigned to two arms (Safe South Africa) versus the control of ordinary usual care. This will be a single blind study. Intervention participants will not be blinded to the condition they are in (the intervention group will receive the intervention first, with the control group given standard usual care. Study staff (e.g. intervention team) will not be blinded to the condition. Study staff (e.g., outcome assessment team) who assess outcomes after the experimental intervention has been delivered will be blinded to the condition participants have been assigned to. Blinding will be broken for data analysis. To reduce the risk of contamination, or that blinding will be broken by participants communicating to each other, we will request that participants in the intervention keep all activities and discussions to themselves. We will also assess whether blinding was successful by checking for contamination at the outcome assessments at 1- and 6-months. There is no chance that participants in the control group would participate mistakenly in the intervention so we assess for contamination in terms of sharing of intervention materials between the intervention and control group. Participants assigned to the control group will be screened for contamination. We will adjust for any contamination effects in analyses. Although this is a feasibility and acceptability trial, thus not designed to be fully powered to measure effects, we set out to create a study design that carefully adheres to elements outlined in the Consolidated Standards of Reporting Trials (CONSORT) Statement.¹⁵⁸ This pilot study adheres to a single blind, randomized pilot trial design with the end goal of informing a future fully powered RCT corresponding to a Phase III clinical trial.

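### The contamination check covers shared materials but not talk, and it names only control boys for a screen at visits that are meant to be blinded

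*Combined protocol and SAP*

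**What the plan says.** All of the rules at issue stand in the Combined protocol and SAP, section E (Methods), Specific Aim 3, Design paragraph.

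- **Who is blinded.** The staff "who assess outcomes after the experimental intervention has been delivered will be blinded to the condition participants have been assigned to".
- **When and why the check is made.** "We will also assess whether blinding was successful by checking for contamination at the outcome assessments at 1- and 6-months".
- **What counts as contamination.** The plan excludes the possibility that a control boy attends the sessions by mistake, "so we assess for contamination in terms of sharing of intervention materials between the intervention and control group".
- **Who is screened.** "Participants assigned to the control group will be screened for contamination". Nothing is said about intervention boys.
- **How the result is used.** The analyses are to be adjusted for contamination.

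The same paragraph recognises that participants may talk to one another. Its response is to ask intervention boys to keep what is done and said in the sessions private.

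Elsewhere under Aim 3, Table 2 lists no contamination instrument, and the Analysis paragraph gives no method for the adjustment. The Assessments text says the outcome questionnaire is self-completed on a smartphone through earphones (A-CASI). The Randomization & Retention paragraph describes permuted-block randomization of adolescents and also places the control arm at another school.

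**The concern.** There are two problems, of unequal strength.

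The first is scope. The programme works through discussion, norms messages and peer action. Section C says of its bystander component: "Positive peer pressure – as exerted through prosocial bystander action – can prevent IPV in others". A control boy who is told what was said in a session has been exposed to that content, yet a question about materials would not record it. The recorded figure could then be too low, and any adjustment built on it would be incomplete. This pilot is also meant to supply effect sizes for planning the next trial, so unrecorded dilution would carry forward.

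The second is the wording of the screen. A procedure named for one arm, at a visit run by staff who should not know the arm, may disclose allocation to them. Whether it does depends on how it is delivered, and the plan does not say.

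**Working it through.** **Scope, from the text.** The Design paragraph names two routes between arms: talk and shared materials. Talk is met with a request for privacy and is not measured. Materials are measured. The adjustment is promised for contamination in general but can rest only on the measured part. If a share *m* of controls is exposed through materials and a further share *t* only through talk, the screen reports *m* when the true share is *m + t*, an undercount of *t*.

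**Unmasking, from the text.**
1. The outcome team is blinded.
2. The check takes place at its 1- and 6-month visits.
3. Controls are named for it and intervention boys are not mentioned.
4. No section says who or what delivers the screen.

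If staff give it, or open it as a separate form for controls, steps 1 to 3 conflict. If it branches silently inside the earphone questionnaire, staff need not see it and there is no conflict. The text does not settle which applies.

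**Size, by assumption.** The documents give no contamination rate, so there is no figure of the plan's to reproduce on this point. The nearest is the Sample Size paragraph's 100 per arm for an effect of 0.50, given without alpha or power. At two-sided 5%, n per arm = 2(z₀.₉₇₅ + z_power)²/d² gives 63 for 80% power, 85 for 90% and 104 for 95%; 100 per arm gives 94%. It serves here only as a reference scale.

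Let *c* be the share of controls that receives the full effect, ignoring clustering. Then:
- apparent d = 0.50 × (1 − c)
- n per arm for 80% power = 2(1.960 + 0.842)²/d² = 15.70/d², rounded up
- power at 100 per arm = Φ(d√50 − 1.960)

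| c (assumed) | apparent d | n per arm, 80% power | power at 100 per arm |
|---|---|---|---|
| 0% | 0.50 | 63 | 94% |
| 10% | 0.45 | 78 | 89% |
| 20% | 0.40 | 99 | 81% |
| 30% | 0.35 | 129 | 70% |
| 40% | 0.30 | 175 | 56% |

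Controls who receive only part of the effect would produce less dilution than the table shows.

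**What an undercount does to an adjustment.** Take c = 30% in truth with only 10% visible through materials (both assumed). The apparent d is 0.35. Rescaling by the recorded share gives 0.35/0.90 = 0.39; rescaling by the true share gives 0.35/0.70 = 0.50. The rescaling is an illustration and not the plan's method, since the plan states none.

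**Precision.** Even a complete screen is imprecise with 30 controls. The 95% Wilson interval is 0% to 11.4% for 0 of 30 and 3.5% to 25.6% for 3 of 30.

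**The case against.** The strongest objection concerns blinding. A reader might infer that the screen is given to controls alone and therefore breaks the blind at the first follow-up visit. The documents do not support that. The plan is silent on the intervention arm, the sentence on timing names no arm, no section has an assessor delivering the screen, and the outcome questions are heard privately through earphones. Only the weaker statement stands: with delivery unspecified, an arm-specific screen could reveal allocation.

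The other-school wording also cuts against the point. If controls attend another school, talk between arms is less likely, and the school itself may tell an assessor the arm whatever happens with the screen. That objection stands as far as it goes, but the same paragraph describes permuted-block randomization of adolescents, so the setting is unresolved. The Design paragraph still treats sharing between arms as possible, screens for it and adjusts for it.

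Two further inferences should be resisted. Section C describes how bystander action is meant to work; it does not establish talk as the main route of contamination. Nor does any section say that the contamination figure will decide whether arms may share a setting in the next trial; the stated uses are the blinding check and the adjustment.

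Finally, intervention boys are supposed to be exposed, so their answers are a weak benchmark for a control boy's answer. That is fair. The main reason to ask both arms is that an identical procedure gives nothing away. It is also fair that loosely worded items would pick up ordinary peer talk or the usual-care brochures and overstate contamination.

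**Conclusion.** The point holds in limited form. The materials-only scope is explicit, and it is at odds with the plan's own recognition of talk as a risk and its promise to adjust; spoken sharing would go unmeasured and contamination could be undercounted. The risk to blinding is conditional on a delivery mode that the plan leaves open. It would be wrong to say that the check itself unblinds the trial.

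The size cannot be fixed from the documents. The dilution from 0.50 to between 0.45 and 0.30 rests on an assumed 10% to 40% of controls receiving the full effect, and separate schools would make cross-arm spread less likely. For a feasibility pilot with exploratory efficacy aims and self-completed outcomes, this is a modest defect that is worth correcting because the correction costs so little.

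**What to change.** 1. Replace the sentence that has control participants screened with one identical exposure block for every participant in both arms. It should be self-completed at the end of the 1- and 6-month A-CASI questionnaire, after all outcome items.
2. Cover both materials seen and session content heard from a study participant. Make the items specific to Safe South Africa content, so that usual-care brochures and ordinary peer talk are not counted.
3. Keep the intention-to-treat estimate without contamination adjustment as the main one. State the method of any contamination-adjusted analysis in advance and present it as secondary.
4. Reconcile the other-school wording with the permuted-block randomization of adolescents. If controls do attend another school, the new block alone will not protect the blind.

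The cost is about two extra minutes at each follow-up visit, within an assessment planned at 1 to 1.5 hours, plus the protocol wording. No extra staff or visits are needed.
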